#### 5.1.2. Deaths, serious AE, and AE leading to discontinuation

The following summaries will be presented:

- Incidence of TESAEs by SOC and PT
- Incidence of treatment-related, treatment-emergent TESAEs by SOC and PT
- TEAEs leading to discontinuation by SOC and PT

Subjects who die, who have SAE and AE leading to discontinuation during the study will be provided in three separate data listings.

## 5.2. Clinical Laboratory Parameters

Laboratory parameters (Table 1) values and the change from baseline will be summarized for each visit.

A by-subject listing of laboratory results will be provided for hematology, coagulation, biochemistry, and urinalysis respectively.

**Table 1: Clinical Laboratory Parameters**

Type	Parameters
Hematology	Basophils, Eosinophils, Erythrocytes, Hematocrit, Hemoglobin, Leukocytes, Lymphocytes, Monocytes, Neutrophils, Platelets
Biochemistry	Alanine Aminotransferase, Albumin, Alkaline Phosphatase, Aspartate Aminotransferase, Bilirubin, Blood Urea Nitrogen, Calcium, Chloride, Cholesterol, Creatinine, Direct Bilirubin, Gamma Glutamyl Transferase, Glucose, Lactate Dehydrogenase, Potassium, Protein, Sodium, Triglycerides, Glutathione
Urinalysis	Ketones, Urine Glucose, Urine Protein, Pregnancy Test
Coagulation	Activated Partial Thromboplastin Time, Prothrombin Time, Intl. Normalized Ratio

## 5.3. Vital Signs

Vital signs (temperature, respiratory rate, systolic blood pressure, diastolic blood pressure, heart rate, oxygen saturation, weight, and BMI) and the change from baseline will be summarized for each visit.

A by-subject level listing of vital signs will be provided.

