### 1.1. Study Design

This is an open-label, Phase 3, safety study of vatiquinone in subjects with inherited mitochondrial disease who either participated in a previous clinical study or treatment plan (rollover subjects) or failed to meet study entry criteria in a prior vatiquinone clinical study (de novo subjects). A target of approximately 200 previously treated vatiquinone subjects and approximately 4 de novo subjects will be enrolled at up to approximately 40 investigational sites worldwide. De novo subjects will receive vatiquinone oral solution (100 mg/mL), up to 200 mg, administered orally or via feeding tube three times a day (TID). Rollover subjects will continue the dosing regimen from their parent study ([Figure 1](#)).

[figure not shown]
The study will include a Screening/Baseline Visit, a Treatment Period, and an End-of-Treatment Visit. For de novo subjects, the study visits will include Screening, Run-in, Baseline, Treatment Period and End-of-Treatment Visit. For subjects that will discontinue early, an Early Termination Visit will be performed 6 weeks after discontinuation.

The duration of vatiquinone treatment will be subject to the following conditions:

[figure not shown]
- The subject has the right to withdraw consent and discontinue vatiquinone at any time.
- The relevant regulatory authority and/or PTC Therapeutics (PTC) may discontinue the study at any time.
- If the subject's condition substantially worsens after initiating vatiquinone treatment in this study, the subject will be carefully evaluated by the investigator in consultation with the PTC medical monitor. The subject will be withdrawn from treatment if continuing would place the subject at risk.
- The investigator may withdraw the subject from vatiquinone treatment if, in the investigator's clinical judgment, it is not in the subject's best interest to continue.
- If the subject is unable to tolerate vatiquinone, the subject will be withdrawn from treatment.

Safety assessments for rollover subjects will be performed at Screening/Baseline and every 6 months. Safety assessments for de novo subjects will be performed at screening, baseline, months 1, 3, 6, and 12, and every 6 months thereafter. Safety assessments will also be collected for all subjects at the End-of-Treatment Visit. Detailed schedule of activities are described in [Table 2](#), [Table 3](#), and [Table 4](#). Diagrams of the study design are provided in [Figure 1](#), [Figure 2](#), and [Figure 3](#).

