### 1.2.2. Exploratory Objectives

Exploratory objectives of the study are:

- To explore the effects of vatiquinone in motor seizure count in subjects previously enrolled in Study PTC743-MIT-001-EP (referred to Study MIT-E hereafter) and in all de novo subjects.
- To explore the effects of vatiquinone based on the Newcastle Pediatric Mitochondrial Disease Scale (NPMDS) in subjects previously enrolled in Study MIT-E, and in all de novo subjects.
- To demonstrate the effects of vatiquinone on health-related quality of life in subjects previously enrolled in Study MIT-E, and in all de novo subjects.

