## **3. GENERAL CONSIDERATIONS**

For continuous variables, mean, standard deviation, median, minimum, maximum, and number of subjects with non-missing data will be provided. For categorical variables, the number and percentage of subjects in each category will be provided.

Day 1 is defined as the first dose date. Study days after day 1 are calculated as: assessment date - first dose date + 1. Study days prior to day 1 are calculated as assessment date - first dose day.

Measurements collected from unscheduled visits, or repeated assessments will be included in the listings only, unless otherwise specified.

The descriptive summaries will be presented by total subjects for safety endpoints. Exploratory and efficacy endpoints will be presented in listings only. All summaries will be based on nominal visits.

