### **3.2. Missing Data Handling**

All analyses will be based on observed data only, and no missing values will be imputed unless otherwise indicated.

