### 6.2. Newcastle Pediatric Mitochondrial Disease Scale (NPMDS)

The NPMDS assessment that corresponds to the subject’s age at the time of informed consent will be used. According to the NPMDS manual, NPMDS Sections 1 to 3 will be assessed by the investigator or subinvestigator (by the same physician during the entire study period, whenever possible), and NPMDS Section 4 will be assessed by the subject’s guardian (by the same guardian during the entire study period, whenever possible) and the subject (if he or she is 7 years of age or older and is able to complete the assessment). The investigator or subinvestigator are to record the dates and results of assessments in the CRF.

Cognitive function in NPMDS Section 3 is not planned to be measured.

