Drug compliance g				X	X	X	X
AE/SAE assessment	X	X	X	X	X	X	X
Prior/Concomitant medication	X	X	X	X	X	X	X

**Abbreviations:** AE, adverse event; CBC, complete blood count; D/C, discontinuation; ECG, electrocardiogram; EOT, End-of-Treatment; ET, Early Termination; NPMDS, Newcastle Pediatric Mitochondrial Disease Scale; PedsQL, Pediatric Quality of Life InventoryTM; SAE, serious adverse event; WOCBP, women of childbearing potential

a Screening will be conducted and completed in a maximum of 42 days (up to 14 days Screening and 28 days Run-in Period) prior to the Baseline Visit. Before the Run-in Period subjects will be trained in diary completion. The Run-in phase and initiation of the seizure diary completed during this phase of the study, will contain a minimum of 28 consecutive days of seizure data collected prior to the Baseline Visit. Ideally the subject will be instructed to start entering diary information the day after screening, so that the requisite number of days can be collected prior to the Baseline Visit. Laboratory tests from within 30 days of Screening are acceptable for entry to the study.

b After the Month 12 visits, subjects will return for on-site visits every 6 months and will have telephone visits every 3 months after the on-site visits, following the Schedule of Assessments for rollover subjects (Table 2).

c Subjects who discontinue vatiquinone prematurely should complete an Early Termination Visit.

d Informed consent will be signed before any study procedures. In case the subject/caregivers/legal guardian cannot attend Screening Visit in the clinic, remote consenting can be obtained.

e Urinalysis by dipstick collection.

- f Drug will be dispensed to the subject every 3 months. For Month 9, the clinical site staff will contact the subject or parent(s)/legal guardian(s) to confirm details and timing of the upcoming study drug shipment. Post-shipment contact will confirm receipt of and condition of study drug.
- g Subjects or parent(s)/caregiver(s) or legal guardian(s) should return all used and unused bottles of vatiquinone as instructed in order to assess study drug compliance.
- h Approximately 7.7 mL of blood will be drawn per visit.

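### SAP Section 5.3 plans BMI and its change from baseline at every visit, but height is scheduled only at screening/baseline, so the scheduled data cannot give a valid post-baseline BMI in subjects still growing

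*SAP*

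**What the plan says.** Section 5.3 (Vital Signs) names eight parameters. For the list ending in "oxygen saturation, weight, and BMI) and the change from baseline will be summarized for each visit", each post-baseline visit is to have a BMI value and a BMI change.

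Section 3 sets the form of the summary. "For continuous variables, mean, standard deviation, median, minimum, maximum, and number of subjects with non-missing data will be provided", and "The descriptive summaries will be presented by total subjects for safety endpoints", so growing and full-grown subjects share one row. Unscheduled or repeated measurements go to listings only, unless otherwise specified.

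Section 3.2 adds: "All analyses will be based on observed data only, and no missing values will be imputed unless otherwise indicated". No rule for deriving post-baseline BMI is given.

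In Appendix 1, Table 2 (rollover subjects) marks height at Screening/Baseline only, while weight is marked in every column. Tables 3 and 4 (de novo subjects, France and Italy) mark height at Screening/Run-in and at Baseline only, again with weight throughout. Footnote b of both tables has de novo subjects, after Month 12, "following the Schedule of Assessments for rollover subjects (Table 2"), which contains no later height.

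Children are expected. Section 6.2 has NPMDS Section 4 completed by the guardian and by "the subject (if he or she is 7 years of age or older and is able to complete the assessment"). The treatment duration categories in Section 4.6 run to 30 months or more.

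**The concern.** BMI is weight divided by height squared, so a BMI at a later visit needs a height at that visit. The SAP plans the derived quantity at every visit, but its own schedule supplies only one of the two inputs after baseline.

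Two readings of the row would mislead if baseline height were reused. Normal growth, which brings weight gain, would appear as a rise in BMI. A real fall in BMI could also be hidden, because a child who grows taller without gaining weight would show no change. The second error matters more in a safety study. Vital signs are a primary endpoint (Section 1.3.1), and Section 5.3 sits under the primary analyses.

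**Working it through.** The plan states no figure to reproduce. The check is whether the planned summary can be produced from the scheduled data, and what follows if a height has to be borrowed.

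**Step 1: is there a post-baseline height?**

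- Rollover subjects (Table 2): none at telephone, 6-monthly, End-of-Treatment or Early Termination visits.
- De novo subjects (Tables 3 and 4): none after Baseline. They then move to Table 2, which has none.
- Unscheduled heights, if recorded: listings only under Section 3.

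No scheduled height therefore feeds the by-visit table after baseline.

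**Step 2: what would the table show?**

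- *Strict reading of Section 3.2.* Height is missing at the visit and is not imputed, so BMI is missing and the number of non-missing values is zero. The row is empty, with no bias.
- *Baseline height carried forward.* With weight w, baseline height h0 and current height h1, the reported value is w/h0² and the true value is w/h1². The overstatement is (h1/h0)² − 1. It is zero if h1 = h0 and positive during growth.

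**Step 3: size under carry-forward.** Baseline height, growth rate and true BMI below are assumptions; none is in the SAP. With steady growth g (cm/year) over t years, h1 = h0 + g·t.

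| Assumed h0, g | 6 months | 12 months | 30 months |
|---|---|---|---|
| any height, 0 cm/year | 0% | 0% | 0% |
| 170 cm, 2 cm/year | (171/170)² − 1 = 1.2% | (172/170)² − 1 = 2.4% | (175/170)² − 1 = 6.0% |
| 130 cm, 4 cm/year | (132/130)² − 1 = 3.1% | (134/130)² − 1 = 6.2% | (140/130)² − 1 = 16.0% |
| 90 cm, 6 cm/year (corner case) | (93/90)² − 1 = 6.8% | (96/90)² − 1 = 13.8% | (105/90)² − 1 = 36.1% |

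If true BMI stays at an assumed 16 kg/m², the false change is 16 times these values. For 130 cm and 4 cm/year it is +0.50, +1.00 and +2.56 kg/m². For the corner case it is +1.08, +2.20 and +5.78 kg/m².

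The masking error, in the same 130 cm example: if weight does not change over 30 months, carried-forward BMI shows a change of 0. True BMI falls by 1 − (130/140)² = 13.8%, that is from 16 to 13.8 kg/m².

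**Step 4: effect on the pooled row.** If a share p of the subjects with data at the visit is still growing, and each has the same false change, the mean change shifts by p × false change. For 130 cm and 4 cm/year at 30 months: 0.25 × 2.56 = 0.64, 0.50 × 2.56 = 1.28 and 0.75 × 2.56 = 1.92 kg/m². The SAP states neither p nor how many subjects reach 30 months.

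**Step 5: can by-visit weight replace BMI?** Only in part. Suppose subjects of 1.00 m and 1.70 m change by +2 kg and −2 kg (assumed). Mean weight change is 0. Mean BMI change at fixed height is (2/1.00² − 2/1.70²)/2 = (2.00 − 0.69)/2 = +0.65 kg/m².

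**The case against.** A reader might infer that the SAP's BMI results will be overstated. The document does not support that. Overstatement requires baseline height to be carried forward, and the SAP nowhere says so; Section 3.2, read strictly, gives blank rows instead. This stands, and the overstatement is conditional for that reason.

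A reader might also infer from the age-7 clause that most subjects are growing. Section 1.2.2 limits the NPMDS objective to former Study MIT-E subjects and de novo subjects, and Section 1.1 targets "approximately 200 previously treated vatiquinone subjects and approximately 4 de novo subjects". The clause shows that children are expected, not what share of about 204 they form. This too stands.

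The protocol, the CRF and the separate table specifications are not shown, and a BMI convention is often placed in such specifications. They could name which height to use. They could not supply heights that the schedule does not call for, and Section 3 would send incidental ones to listings.

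The magnitudes rest wholly on assumed inputs, and the effect at the first 6-monthly visit is small (about 3% in the 130 cm example). Both are true. The direction under carry-forward does not depend on those inputs.

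Finally, a footnote naming the height used would be lighter than deleting the row. It would disclose the bias but leave it in the table.

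**Conclusion.** The point holds in a limited form. Section 5.3 plans a by-visit BMI change that the schedule in Appendix 1 cannot support in subjects still growing. Following the SAP gives either an empty row or, if baseline height is reused, a row biased upward by (current height / baseline height)² − 1 in those subjects and correct in full-grown ones. The mismatch itself is certain from the document. The percentages illustrate one branch only, and the pooled effect is unknown because the share still growing is not stated.

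This is an optional improvement. BMI is one of eight descriptive vital-sign parameters, weight is summarized beside it, subject-level listings are planned, and the study has no formal hypothesis. No test, sample size or decision rule depends on the row.

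**What to change.** In Section 5.3, delete BMI from the list of parameters summarized by visit and as change from baseline, and add one sentence: *BMI is summarized at baseline only (Section 4.3).* Keep the by-visit weight summary as planned, and remove the BMI row from the table shell.

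The cost is one sentence and one shell row, with no new data. The table has one fewer descriptive parameter, and mean BMI change cannot be recovered from mean weight change (Step 5 of the working).

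Keeping by-visit BMI only for subjects full-grown at baseline would also avoid the bias. It would need a definition of full-grown that the SAP does not contain, and a statement that baseline height is used.

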### **3.1. Baseline**

For safety and efficacy endpoints, baseline will be defined as the last measurement prior to or on the date of first dose date in PTC743-CNS-005-LSEP.

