### 4.3. Demographic and Baseline Characteristics

Demographics and baseline characteristics including age, sex, race, ethnicity, region, country, height, weight, and body mass index (BMI) will be summarized for safety population.

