### 4.6. Duration of Treatment with Study Drug

Duration of treatment with study drug will be calculated as number of days from the date of the first dose in PTC743-CNS-005-LSEP to the date of the last dose, inclusive.

Duration of treatment will be summarized for safety population and will also be summarized by the following categories.

- <6 months
- $\geq 6$  to <12 months
- $\geq 12$  to <18 months
- $\geq 18$  to <24 months
- $\geq 24$  to <30 months
- $\geq 30$  months

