## APPENDIX 1. SCHEDULE OF EVENTS

**Table 2:** Schedule of Assessments – Rollover Subjects

Study Period	Screening/Baseline a	Treatment		EOT Visit	ET (6 Weeks After D/C) b
Study Month	Day 1	Telephone Visits 3 Months (84±7 Days) After On-Site Visits	Every 6 Months (168±7 Days)		
Informed consent	X c				
Demographics	X				
Medical history	X				
Vital signs	X		X	X	X
Height	X				
Weight	X	X d	X	X	X
Physical examination	X		X	X	X
12-Lead ECG	X		X	X	X
Urine pregnancy test (WOCBP) l	X		X	X e	X
Hematology (CBC w/ differential)	X m		X m	X m	X m
Serum chemistry	X m		X m	X m	X m
Coagulation panel	X m		X m	X m	X m
Urinalysis f	X		X	X	X
NPMDS g	X		X	X	X
CarerQoL-7D g	X h		X	X	X
PedsQL g	X h		X	X	X
Drug dispensed i	X	X	X		
Pre-/post-shipment contact j		X			
Drug compliance k			X	X	X
AE/SAE assessment	X	X d	X	X	X
Prior/concomitant medication	X	X d	X	X	X

**Abbreviations:** AE, adverse event; CBC, complete blood count; D/C, discontinuation; ECG, electrocardiogram; EOT, End-of-Treatment; ET, Early Termination; NPMDS, Newcastle Pediatric Mitochondrial Disease Scale; PedsQL, Pediatric Quality of Life Inventory™; SAE, serious adverse event; Study MIT-E, Study PTC743-MIT-001-EP; WOCBP, women of childbearing potential

a On-site visit applicable to all subjects rolling over to this study. For subjects rolling over from Study MIT-E, the Screening/Baseline Visit in this study will also be the Week 72 visit in Study MIT-E.

b Subjects who discontinue vatiquinone prematurely should complete an ET Visit.

c Informed consent will be signed before any study procedures. In case the subject/caregivers cannot attend the Screening/Baseline Visit in the clinic, remote consenting can be obtained.

d Clinical site staff will contact subject or parent(s)/legal guardian(s) every 3 months (by telephone if there is no clinic visit) to assess AEs, weight, and concomitant medications.

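### Weight and BMI are summarized only as pooled raw change from baseline in an uncontrolled study that includes growing children, so normal growth can mask poor weight gain

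*SAP*

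**What the plan says.** Section 1.3.1 makes vital signs a primary endpoint. Section 5.3 counts weight and BMI among them and plans observed values and raw change: "oxygen saturation, weight, and BMI) and the change from baseline will be summarized for each visit". The only other vital-sign output in that section is a by-subject listing.

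Section 3 sets the grouping: "The descriptive summaries will be presented by total subjects for safety endpoints". No age strata are given. Under section 3.1, "baseline will be defined as the last measurement prior to or on the date of first dose date in PTC743-CNS-005-LSEP". Section 4.6 states "Duration of treatment will be summarized for safety population and will also be summarized by the following categories", and the list that follows ends in an open category of 30 months or more.

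Section 1.1 describes an open-label study with no comparator. That children take part is clear but only indirectly stated: a pediatric disease scale and a pediatric quality-of-life questionnaire are used, guardians act as raters, and section 6.2 has the subject rate Section 4 of the scale only "if he or she is 7 years of age or older and is able to complete the assessment". No age range and no share of children is given.

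In Appendix 1, weight is recorded throughout treatment. Height is marked only at Screening/Baseline for rollover subjects (Table 2) and only at screening and baseline for de novo subjects (Tables 3 and 4).

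**The concern.** A growing child is expected to gain weight, so the adverse direction is gaining too little. On the kilogram scale, too little gain is a zero or small positive number, which reads as harmless. When such values are averaged with the normal gains of other children, the mean change stays positive. With a fixed baseline the growth component increases at every later visit, and with no control arm nothing in the table shows how much gain to expect.

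At stake is whether a primary safety table could show a growth deficit if there were one. BMI looks like a natural safeguard because it adjusts for size. Without a current height, however, it cannot do that.

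**Working it through.** The SAP gives no figure on this point, so there is none to reproduce. The growth rates, shares, deficits and heights below are assumptions, shown as ranges.

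**1. Time span.** 30 months is 2.5 years. Five visits at the nominal 168-day spacing of Table 2 come to 5 × 168 = 840 days, about 2.3 years. The calculation uses 2.5 years; on 2.3 years each growth term is about 8% smaller.

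**2. Contribution of growth to the mean weight change.** Growth term = share still growing × kg per year × 2.5.

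| Assumed gain | All growing | Half growing |
|---|---|---|
| 1 kg/year | 1 × 1 × 2.5 = +2.5 kg | 0.5 × 1 × 2.5 = +1.25 kg |
| 2 kg/year | 1 × 2 × 2.5 = +5.0 kg | 0.5 × 2 × 2.5 = +2.5 kg |
| 3 kg/year | 1 × 3 × 2.5 = +7.5 kg | 0.5 × 3 × 2.5 = +3.75 kg |

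These are also the break-even values: any mean deficit smaller than the entry leaves the pooled mean change positive.

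**3. What a deficit looks like in the table.** Observed mean = growth term − mean deficit. For an assumed mean deficit of 2 kg over all subjects:

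- All growing: 2.5 − 2 = +0.5 kg; 5.0 − 2 = +3.0 kg; 7.5 − 2 = +5.5 kg.
- Half growing: 1.25 − 2 = −0.75 kg; 2.5 − 2 = +0.5 kg; 3.75 − 2 = +1.75 kg.

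The mean stays positive in five of the six cases. In the sixth (half growing, slow growth) the deficit shows as a negative mean.

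**4. BMI on an outdated height.** If on-treatment BMI is computed as current weight divided by baseline height squared, the change in BMI is the weight change divided by a constant for each subject. It adds no information beyond weight. To see the size, assume a true BMI that stays at 15 kg/m², a starting height of 1.0 to 1.4 m and height growth of 3 to 7 cm per year. Spurious change = 15 × (height at 30 months ÷ baseline height)² − 15.

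- Smallest: 1.4 m, 3 cm/year. Height becomes 1.475 m; 15 × (1.475/1.4)² − 15 = about +1.7 kg/m².
- Largest: 1.0 m, 7 cm/year. Height becomes 1.175 m; 15 × 1.175² − 15 = about +5.7 kg/m².

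BMI would therefore appear to rise although true BMI had not changed.

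**5. Data for a better scale.** Section 4.3 lists "age, sex, race, ethnicity, region, country, height, weight, and body mass index (BMI) will be summarized for safety population", and weight is measured at the visits. Weight-for-age-and-sex needs only age, sex and weight. BMI-for-age would also need height on treatment, which is not scheduled.

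**The case against.** The strongest reply is that the table shows more than a mean. Section 3 also requires the standard deviation, median, minimum and maximum. A true loss would give a negative minimum and appear in the listing. If many children gained nothing, the minimum would reach zero and the median would be pulled down. Weight and adverse events are also assessed every 3 months, so poor growth that an investigator reports would enter the adverse-event tables. The study is descriptive, with no formal hypothesis resting on the mean. Without a control arm, even a falling z-score could reflect progression of the disease.

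Much of this stands. A reader might infer that growth determines the weight result, or that a poor gain would be wholly indistinguishable from normal. The documents support neither, because the age mix is unknown and the other statistics and outputs remain. The age rule in section 6.2 concerns a scale used only in subjects from Study MIT-E and in de novo subjects, of whom about 4 are planned. It does not describe the ages of the other rollover subjects among the roughly 200 targeted. Pregnancy testing suggests that some older subjects were expected.

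A reader might also extend the argument to heart rate, respiratory rate and blood pressure. These may drift with age, but nothing in the SAP shows that such drift would hide harm. Growth gives no reason for temperature or oxygen saturation to shift.

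What the reply does not remove is failure to gain. In a pooled column or a listing without an age reference, a flat weight in a child looks the same as a stable weight in an adult. Adverse-event reporting depends on someone having already recognized the problem.

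**Conclusion.** The point holds for weight and BMI, as a weakness in the chosen summary measure and not as an error or contradiction in the SAP. Pooled raw change from a fixed baseline, with open-ended follow-up and no comparator, carries an upward growth component that can mask poor weight gain. Over 2.5 years that component is 2.5 to 7.5 kg if all subjects are growing and 1.25 to 3.75 kg if half are, at an assumed 1 to 3 kg per year. With few children or slow growth it would be small, and a deficit could still show. The 30-month category shows that such durations were provided for, not how many subjects reach them. BMI change offers no independent check, because no current height is scheduled after baseline. This is a worthwhile, low-cost improvement to a primary safety summary.

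**What to change.** In section 5.3, for subjects below a stated age:

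- Add the weight-for-age-and-sex z-score and its change from baseline by visit, using a named growth reference and age at the visit. A child who follows the reference contributes a change of about zero, so poor gain shows as a negative change.
- Keep kilograms for adults and for the listings.
- Do not summarize BMI change for growing subjects unless a current height exists.

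This needs SAP wording and a derived variable from age, sex and weight, with no new visits. The costs are the choice of a growth reference and an age cut-off, both to be fixed before database lock. The z-score does not isolate a drug effect: without a control arm, a fall may also reflect disease progression, and the text accompanying the table should say so.
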